#### Assessment of Causality

- The Investigator is obligated to assess the relationship between the study drug and each occurrence of each AE or SAE. An Investigator causality assessment must be provided for all AEs (both nonserious and serious). This assessment must be recorded in the eCRF and on any additional forms, as appropriate. The definitions for the causality assessments are as follows:
  - Not related: There is no reasonable possibility the study intervention caused the adverse event.
    - The adverse event has a more likely alternative etiology; it may be due to underlying or concurrent illness, complications, concurrent treatments, or effects of another concurrent drug.
    - The event does not follow a reasonable temporal relationship to administration of the study intervention.
  - Related: There is a reasonable possibility the study intervention caused the adverse event.
    - The adverse event has a temporal relationship to the administration of the study intervention.
    - The event does not have a likely alternative etiology.
    - The event corresponds with the known pharmaceutical profile of the study intervention.
  - There is improvement on discontinuation and/or reappearance on rechallenge.
- The Investigator will use clinical judgment to determine the relationship.
- Alternative causes, such as underlying disease(s), concomitant therapy, and other risk factors, as well as the temporal relationship of the event to study drug administration will be considered and investigated.
- This protocol will use the current Investigator's Brochure as the Reference Safety Document. The expectedness and reporting criteria of an SAE will be determined by Alexion, based on the Reference Safety Document. The Investigator will also consult the Investigator's Brochure (IB) in his/her assessment.
- For each AE/SAE, the Investigator must document in the medical notes that he/she has reviewed the AE/SAE and has provided an assessment of causality.
  - There may be situations in which an SAE has occurred, and the Investigator has minimal information to include in the initial report to Alexion. However, it is very important that the Investigator always makes an assessment of causality for every event before the initial transmission of the SAE data to Alexion or designee.
- The Investigator may change his/her opinion of causality in light of follow-up information and send a SAE follow-up report with the updated causality assessment.
- The causality assessment is one of the criteria used when determining regulatory reporting requirements.

#### Follow-up of Adverse Events and Serious Adverse Events

- The Investigator is obligated to perform or arrange for the conduct of supplemental measurements and/or evaluations as medically indicated or as requested by Alexion to elucidate the nature and/or causality of the AE or SAE as fully as possible. This may include additional laboratory tests or investigations, histopathological examinations, or consultation with other health care professionals.
- New or updated information will be recorded in the originally completed eCRF.
- The Investigator will submit any updated SAE data to Alexion within 24 hours of receipt of the information.

# **10.4.** Appendix 4: Pregnancy Information

#### 10.4.1. Definitions

#### 10.4.1.1. Woman of Childbearing Potential

A woman is considered fertile following menarche and until becoming post-menopausal unless permanently sterile (see below).

If fertility is unclear (eg, amenorrhea in adolescents or athletes) and a menstrual cycle cannot be confirmed before first dose of study drug, additional evaluation should be considered.

#### 10.4.1.2. Women in the following categories are not considered WOCBP

- 1. Premenarchal
- 2. Premenopausal female with 1 of the following:
  - Documented hysterectomy
  - Documented bilateral salpingectomy
  - Documented bilateral oophorectomy
- For individuals with permanent infertility due to an alternate medical cause other than the above, (eg, mullerian agenesis, androgen insensitivity), Investigator discretion should be applied to determining study entry.
- Note: Documentation can come from the site personnel's: review of the participant's medical records, medical examination, or medical history interview.
- 3. Postmenopausal female
  - A postmenopausal state is defined as no menses for 12 months without an alternative medical cause.
    - A high follicle stimulating hormone (FSH) level in the postmenopausal range may be used to confirm a postmenopausal state in women not using hormonal contraception or hormonal replacement therapy (HRT). However, in the absence of 12 months of amenorrhea, confirmation with more than one FSH measurement is required.
  - Females on HRT and whose menopausal status is in doubt will be required to use one of the non-estrogen hormonal highly effective contraception methods if they wish to continue their HRT during the study. Otherwise, they must discontinue HRT to allow confirmation of postmenopausal status before study enrollment.

### **10.4.2.** Contraception Guidance

Before receiving study drug, female participants who consider themselves to be postmenopausal must provide evidence of menopause based on a combination of amenorrhea for at least 1 year and increased serum FSH level (> 30 IU/L).

Women of childbearing potential must use a highly effective or acceptable method of contraception (as defined below) starting at Screening and continuing for at least 8 months after the last dose of study drug.

Highly effective contraceptive methods are:

- 1. Intrauterine device in place for at least 6 weeks prior to first dose of study drug.
- 2. Progestogen-only hormonal contraception associated with inhibition of ovulation (either oral, injectable, or implantable) for at least 6 weeks prior to first dose of study drug.
- 3. Intrauterine progestogen releasing system for at least 6 weeks prior to first dose of study drug.
- 4. Bilateral tubal occlusion for at least 6 weeks prior to first dose of study drug.
- 5. Combined (estrogen- and progestogen-containing) hormonal contraception (either oral, intravaginal, or transdermal) for at least 6 weeks prior to first dose of study drug.
- 6. Surgical sterilization of the male partner (medical assessment of azoospermia is required if vasectomy was performed within the prior 6 months prior to the first dose of study drug). Male partner is still required to use condom during sexual intercourse.
- 7. Sexual abstinence for female participants:
  - Sexual abstinence is considered a highly effective method only if defined as refraining from heterosexual intercourse. In this study, abstinence is only acceptable if consistent with the participant's preferred and usual lifestyle. Abstinent female participants must refrain from heterosexual intercourse for at least 8 months after the final dose of study drug.

Other methods of contraception that are not considered highly effective for female participants but are acceptable birth control methods that result in a failure rate of more than 1% per year include:

- Progestogen-only oral hormonal contraception, where inhibition of ovulation is not the primary mode of action
- Male or female condom with or without spermicide
- Cap, diaphragm, or sponge with spermicide
- A combination of male condom with cap, diaphragm, or sponge with spermicide (double-barrier methods)

Female participants must not donate ova from the Day 1 Visit at least until 8 months after their final dose of study drug.

The following methods of contraception are considered unacceptable in this study:

- Periodic abstinence (calendar, symptothermal, or post ovulation methods)
- Withdrawal (coitus interruptus)
- Spermicides only
- Lactational amenorrhea method

• Female condom and male condom should not be used together

## **10.4.3. Pregnancy Testing**

Participants of childbearing potential should only be included after a menstrual period and a negative highly sensitive serum pregnancy test.

Additional pregnancy testing should be performed per the time points specified in the SoA (Section 1.3).

Pregnancy testing will be performed whenever a menstrual cycle is missed or when pregnancy is otherwise suspected.

### **10.4.4.** Collection of Pregnancy Information

### 10.4.4.1. Male Participants with Partners who Become Pregnant

- The Investigator will attempt to collect pregnancy information on any male participant's female partner who becomes pregnant while the male participant is in this study. This applies only to male participants who receive study drug.
- After obtaining the necessary signed informed consent from the pregnant female partner directly, the Investigator will record pregnancy information on the appropriate form and submit it to Alexion within 24 hours of learning of the partner's pregnancy. The female partner will also be followed to determine the outcome of the pregnancy. Information on the status of the mother and child will be forwarded to Alexion. Generally, the follow-up of the baby will be no longer than 3 months after the birth of the baby. Any termination of the pregnancy will be reported regardless of fetal status (presence or absence of anomalies) or indication for the procedure.

### 10.4.4.2. Female Participants who Become Pregnant

- The Investigator will collect pregnancy information on any female participant who becomes pregnant while participating in this study. The initial Information will be recorded on the appropriate form and submitted to Alexion within 24 hours of learning of a participant's pregnancy.
- The participant will be followed to determine the outcome of the pregnancy. The Investigator will collect follow-up information on the participant and the neonate and the information will be forwarded to Alexion. Generally, follow-up of the baby will occur at 3 months after birth. Any termination of pregnancy will be reported, regardless of fetal status (presence or absence of anomalies) or indication for the procedure.
- While pregnancy itself is not considered to be an AE or SAE, any pregnancy complication or elective termination of a pregnancy for medical reasons will be reported as an AE or SAE. A spontaneous abortion (occurring at < 22 weeks gestational age) or still birth (occurring at > 22 weeks gestational age) is always considered to be an SAE and will be reported as such. Any post-study pregnancy related SAE considered reasonably related to the study drug by the Investigator will be reported to Alexion as described in Section 8.3.5. While the investigator is not

obligated to actively seek this information in former study participants, he or she may learn of an SAE through spontaneous reporting.

• Any female participant who becomes pregnant while participating in the study will discontinue study drug, and each pregnancy will be followed to term and Alexion notified regarding the outcome.

# 10.5. Appendix 5: Questionnaires PNH Symptoms and Health Resource Utilization

## 10.5.1. PNH Patient-Reported Symptoms questionnaire

V10.000 PROD 24MAY2018: Review

PNH Symptoms Patient Questionnaire completed?	Yes
	∧ No O
Date Completed (dd/mon/yyyy)	
Below are listed symptoms that are sometimes associated with PNH.	Read each carefully.
If you have had the symptom in the past week, please indicate ho SEVERE it was, and how much it DISTRESSED or BOTHERED	w OFTEN you have had it, how you.
If you DID NOT HAVE the symptom, Select DID NOT HAVE.	 
During the past week did you have any of the following	1 Yellow discoloration of eyes
symptoms:	2. Discoloration of urine (in the
X	3 Chest Pain
	4 Shortness of breath
	5. Headache
	6. Fatigue
	7. Abdominal pain
	8. Confusion
	9. Erectile Dysfunction (if
	applicable)
	10. Trouble swallowing
	11. Other
	12. Other
If other, specify	
DID NOT HAVE	
If YES, how often did you have it?	Rarely
	Occasionally
	Frequently
	Almost Constantly
If YES, how severe was it usually?	Slight
	Moderate
	Severe
	0

PNH Symptoms Patient Questionnaire completed?	Yes
	Nº○
Date Completed (dd/mon/yyyy)	
Below are listed symptoms that are sometimes associated with	h PNH. Read each carefully.
If you have had the symptom in the past week, please indi SEVERE it was, and how much it DISTRESSED or BOT	cate how OFTEN you have had it, how HERED you.
If you DID NOT HAVE the symptom, Select DID NOT H	AVE.
During the past week did you have any of the following	I Yellow discoloration of eyes
symptoms:	2. Discoloration of urine (in the
X	3. Chest Pain
$\sim$	4. Shortness of breath
	5. Headache
	6. Fatigue
	7. Abdominal pain
0	8. Confusion
	9. Erectile Dysfunction (if
	applicable)
	10. Trouble swallowing
	11. Other
	12. Other
If other, specify	
DID NOT HAVE	
If YES, how often did you have it?	Rarely
	Occasionally
	Frequently
	Almost Constantly
If YES, how severe was it usually?	Slight
	Moderate
	Severe
	0

	Very Severe
If YES, how much did it distress or bother you?	Not at all
	Alittle bit
	Somewhat
	Quite a bit
	Very much
During the past week did you have any of the following	Vallow discoloration of aver
symptoms?	2 Discoloration of wine (in the
	morning
~~~~~~~~~~~~~~~~~~~~~~~~~~~~~~~~~~~~~~	3. Chest Pain
	4. Shortness of breath
	5. Headache
	6. Fatigue
	7. Abdominal pain
	8. Confusion
0	9. Erectile Dysfunction (if
	applicable)
	12. Other
If other, specify	0
DID NOT HANT	
If YES, how often did you have it?	Rarely
6	Occasionally
- )	Frequently
	Almost Constantly
If YES, how severe was it usually?	Slight
	Moderate
	Severe
	Very Severe
If YES, how much did it distress or bother you?	Not at all
	0

	A little bit
	Somewhat
	Quite a bit
	Very much
During the past week did you have any of the following	1. Yellow discoloration of eyes
symptoms?	2. Discoloration of urine (in the
	morning)
A	3. Chest Pain
 	4. Shortness of breath
	5. Headache
	6. Fatigue
$\sim$	7. Abdominal pain
	8. Confusion
$\sim$	9. Erectile Dysfunction (if
	applicable)
	10. Trouble swallowing
	11. Other
	12. Other
If other, specify	
DID NOT HAVE	
If YES, how often did you have it?	Rarely
	Occasionally
	Frequently
60	Almost Constantly
If YES, how severe was it usually?	Slight
	Moderate
	Severe
	Very Severe
If YES, how much did it distress or bother you?	Not at all
	A little bit
	Somewhat
	0

	Quite a bit
	Verymuch
During the past week did you have any of the following	1. Yellow discoloration of eyes
symptoms?	2. Discoloration of urine (in the
	morning)
	3. Chest Pain
	4. Shortness of breath
	5. Headache
	6. Fatigue
	7. Abdominal pain
	8. Confusion
	
 
9. Erectile Dysfunction (if)
 

	applicable)
	10. House swanowing
	11. Other
	12. Other
If other, specify	
DID NOT HAVE	
If YES, how often did you have it?	Rarely
$\sim$	Occasionally
	Frequently
	Almost Constantly
If YES, how severe was it usually?	Slight
5	Moderate
	Severe
	Very Severe
If YES, how much did it distress or bother you?	Not at all
	A little bit
	Somewhat
	Quite a bit
	Very much

During the past week did you have any of the following	1. Yellow discoloration of eves
symptoms?	2 Discoloration of uting (in the
	morning)
	3. Chest Pain
	4. Shortness of breath
	5. Headache
	6. Fatigue
	7. Abdominal pain
0	8. Confusion
	9. Erectile Dysfunction (if
X	applicable)
	12 Other
Kathar maile	
If other, specify	
DID NOT HAVE	
If VES, how offen did you have if	Rarely
	Our institution
	Occasionally
	Occasionally Frequently
	Occasionally Frequently Almost Constantly
If YES, how severe was it usually?	Occasionally Frequently Almost Constantly Slight
If YES, how severe was it ubually?	Occasionally Frequently Almost Constantly Slight Moderate
If YES, how severe was it usually?	Occasionally Frequently Almost Constantly Slight Moderate Severe
If YES, how severe was it usually?	Occasionally Frequently Almost Constantly Slight Moderate Severe Very Severe
If YES, how much did it distress or bother you?	Occasionally Frequently Almost Constantly Slight Moderate Severe Very Severe Not at all
If YES, how much did it distress or bother you?	Occasionally Frequently Almost Constantly Slight Moderate Severe Very Severe Not at all A little bit
If YES, how much did it distress or bother you?	Occasionally Frequently Almost Constantly Slight Moderate Very Severe Very Severe Not at all A little bit Somewhat
If YES, how severe was it usually? If YES, how much did it distress or bother you?	Occasionally Frequently Almost Constantly Slight Moderate Severe Very Severe Very Severe Not at all A little bit Somewhat Quite a bit
If YES, how severe was it usually? If YES, how much did it distress or bother you?	Occasionally Frequently Almost Constantly Slight Moderate Severe Very Severe Very Severe Not at all A little bit Somewhat Quite a bit Very much
If YES, how severe was it usually? If YES, how much did it distress or bother you?	Occasionally Frequently Almost Constantly Slight Moderate Severe Very Severe Very Severe Not at all A little bit Somewhat Quite a bit Very much

	3. Chest Pain
	4. Shortness of breath
	5 Headache
	6. Fatigue
	Abdominal pain
	8. Confusion
	9. Erectile Dysfunction (if
	applicable)
	10. Trouble swallowing
	11. Other
	12. Other
If other, specify	 
DID NOT HAVE	
If YES, how often did you have it?	Raraly
	Occasionally
	Ensurativo
	Almost Constantly
\ (Z)	Almost Constantly
If YES, how severe was it usually?	Slight
	Moderate
$\sim$	Severe
$\sim$	Very Severe
If YES, how much did it distress or bother you?	Not at all
~ ^ ^	A little bit
6	Somenthat
	Quite a hit
	Versenach
	Very Inucio
During the past week did you have any of the following	
 
Yellow discoloration of eyes
 

symptoms?	2. Discoloration of urine (in the
	morning)
	3. Chest Pain
	4. Shortness of breath
	0

	5. Headache
	6 Fatigue
	7. Abdominal pain
	Confusion
	9. Erectile Dysfunction (if
	applicable)
	10 Trouble swallowing
	11. Other
۵.	12. Other
If other, specify	
DID NOT HAVE	
If YES, how often did you have it?	Rarely
	Oceasionally
	Frequently
	Almost Constantly
If YES, how severe was it usually?	Slight
	Moderate
	Severe
	Very Severe
If YES, how much did it distress or bother you?	Not at all
	A little bit
	Somewhat
C'O'	Quite a bit
5	Very much
During the past week did you have any of the following	1. Yellow discoloration of eves
symptoms?	2. Discoloration of urine (in the
	morning)
	3. Chest Pain
	4. Shortness of breath
	5. Headache
	6. Fatigue
	0

	7 Abdominal pain
	Conferier
	a Francis De Constant
	9. Erechle Dysfunction (if
	10 Trouble swallowing
	11. Other
	12. Other
If other, specify	
DID NOT HAVE	
If YES, how often did you have it?	Rarely
	Occasionally
	Frequently
$\mathbf{N}$	Almost Constantly
If YES, how severe was it usually?	Slight
	Moderate
	Severe
	Very Severe
If YES, how much did it distrets or bother you?	Not at all
	A little bit
$\sim$	Somewhat
	Quite a bit
	Very much
During the past week did you have any of the following	1. Yellow discoloration of eves
symptoms?	2. Discoloration of urine (in the
	morning)
	3. Chest Pain
	4. Shortness of breath
	5. Headache
	6. Fatigue
	7. Abdominal pain
	8. Confusion
	0

-----

	9. Erectile Dysfunction (if
	applicable)
	10. Trouble awallowing
	tl. Other
	12. Other
If other, specify	
DID NOT HAVE	
If YES, how often did you have it?	Rarely
	Occasionally
	Frequently
	Almost Constantly
INVES have and it must be?	
If 12.5, now severe was it usually:	Sugnt
	Midderate
$\sim$	Severe
	Very Severe
If YES, how much did it distress or bother you?	Not at all
	A little bit
	Somewhat
	Quite a bit
$\sim$	Very much
	0
During the past week did you have any of the following	
 
Yellow discoloration of eyes
 

symptoms?	2. Discoloration of urine (in the
 	morning)
	5. Clest Pall
	4. Shortness of breath
	5. Headache
	6. Fatigue
	7. Abdominal pain
	8. Confusion
	9. Erectile Dysfunction (if
	applicable)

	10. Trouble swallowing
	11 Other
If other, specify	
DID NOT HAVE	
If YES, how often did you have it?	Rarely
	Occasionally
	Frequently
	Almost Constantly
If YES, how severe was it usually?	Slight
	Moderate O
	Severe
	Very Severe
If YES, how much did it distress or bother you?	Not at all
	A little bit
0	Somewhat
	Quite a bit
	Very much
During the past week did you have any of the following	1. Yellow discoloration of eyes
symptoms?	2. Discoloration of urine (in the
	morning)
C'0	5. Clest Pain
$\sim$	4. Shortness of oreath
	6 Entrano
	7 Abdominal nain
	8 Confusion
	9. Erectile Dysfunction (if
	applicable)
	10. Trouble swallowing
	11. Other
#### V10.000 PROD 24MAY2018: Review

Form: PNH Symptoms Patient Questionnaire Generated On: 11 Jun 2018 17:23:55

	12. Other
If other, specify	
DID NOT HAVE	
If YES, how often did you have it?	Rarely
	Occasionally
	Frequently
	Almost Constantly
If YES, how severe was it usually?	Slight
ç	Moderate
	Severe
	Very Severe
If YES, how much did it distress or bother you?	Not at all
	A little bit
	Somewhat
	Quite a bit
0	Very much
0	
5	

### 10.5.2. Health Resource Utilization questionnaire

Resource utilization patient questionnaire completed?	0	Yes
Date Completed (dd/mon/yyyy)	2	- 7.92
This questionnaire asks about health care services you may have received during	the past month.	
1. How many times within the past month have you visited your health care provider primarily for treatment of your PNH? Enter "0" if you have not seen a physician for PNH within the past month.		
2. How many times within the past month have you gone to an Emergency Room primarily for treatment of your PNH? Enter "0" if you have not seen visited an Emergency Room for PNH within the past month.		
3. How many times within the past month have you been admitted to a Hospital primarily for treatment of your PNH? Enter "0" if you have not been admitted to a hospital for PNH within the past month.		
4. How many times within the past month have you had darkened urine? Enter "0" if you have not experienced darkened urine within the past month		
5. How many times within the past month did you miss work as a result of symptoms of PNH? Enter "0" if you have not missed work as a result of PNH symptoms within the past month.		
5	o Excelle o Very G	ent Jood
general would you say your health is:	o Good o Fair o Poor	

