### **Overall Design**

This is a Phase 4, single-arm, open-label study to evaluate the efficacy and safety of ravulizumab in adult participants with PNH who switch from eculizumab 1200 mg every 2 weeks (q2w; ie, above the recommended dose) to ravulizumab (at the recommended dose).

The study will consist of a Screening Period of approximately 3 months and a Treatment Period of 351 days. All participants must provide informed consent prior to any procedures at the first Screening visit. All participants must have been prescribed and are receiving a stable dose of eculizumab 1200 mg q2w for at least 3 months prior to screening. During Screening, eculizumab may be administered at the participant's home at the discretion of the Investigator. During screening, participants will continue to receive eculizumab 1200 mg q2w, and blood samples will be collected for PD parameters and lactate dehydrogenase (LDH) levels.

Eligible participants will receive a loading dose of ravulizumab on Day 1, followed by maintenance doses on Day 15 and every 8 weeks (q8w), administered by intravenous (IV) infusion. Ravulizumab loading and maintenance doses will be based on participants' body weight per approved dose regimen. Ravulizumab dosing will be administered in the clinic by a trained member of the site study team; patients may have the option to receive study drug remotely at a medical facility that is located near the patient's home or at the patient's home by a qualified healthcare personnel.

The schedule of study visits and assessments is shown in Section 1.3.

An interim analysis will be performed on Day 183.

**Disclosure Statement:** This is a single-arm, open-label study.

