### **1.3.** Schedules of Activities

#### Table 1: Schedule of Study Visits and Assessments: Screening Visit Through Confirmation Visit

Period			Scr	eening			Notes		
Study Day	-85	-71	-57	-43	-29	-15			
Window (day)	± 2	± 2	± 2	± 2	± 2	± 2	All study assessments for a given Study Day must be completed on the same day as the study visit. The window of $\pm 2$ days is relative to Day 1 and allows for the Study Visit to occur $\pm 2$ days from the indicated study day		
Informed consent	Х								
Inclusion and exclusion criteria	Х								
Confirmation of meningococcal vaccination				Х			Refer to Section 6.5.1 for details		
Abbreviated physical examination	Х		Х		Х		Refer to Section 8.2.1 for details		
Height	Х								
Weight	Х		Х		X				
Medical history including PNH and eculizumab dosing history	Х								
Serum or urine pregnancy test	Х		Х		Х		Refer to Section 8.3.5 for details. Serum pregnancy test at Day -85, Urine pregnancy test at all other visits		
HIV testing	Х								
Chemistry including LDH	Х		Х		Х		Sample to be collected within 24 hours of or immediately prior to a scheduled dose of study drug (trough) and not from a heparinized line.		
Hematology including free hemoglobin and coagulation	Х		Х		Х		Blood will be collected predose and not from a heparinized line.		
Urinalysis and urine chemistry	Х		Х		X		Urine will be collected predose on dosing days.		
Safety 12-lead ECG	Х						Participants must be supine for approximately 5 to 10 minutes before ECG collection and remain supine but awake during ECG collection. Refer to Section 8.2.3 for details		
Vital signs	Х		Х		Х		Will be measured after the participant has been resting for at least 5 minutes. Refer to Section 8.2.2 for details		
PNH clone size	Х						WBC (granulocyte and monocyte) and RBC clone size measured by high-sensitivity flow cytometry at Screening; RBC clone size only at Screening		
Record transfusions and transfusion parameters	X	X	Х	Х	Х	Х	Transfusions given during and between visits will be recorded. This can be optionally performed by a phone call on Days -71, -43, and -15		

Period			Scre	ening			Notes		
Study Day	-85	-71	-57	-43	-29	-15			
Window (day)	± 2	± 2	± 2	± 2	± 2	± 2	All study assessments for a given Study Day must be completed on the same day as the study visit. The window of $\pm 2$ days is relative to Day 1 and allows for the Study Visit to occur $\pm 2$ days from the indicated study day		

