PNH symptomatology	Х	Х	Х	Х	Х	Х	Investigator assessed and reported. Refer to Section 8.1.3 for details. This can be optionally performed by a phone call on Days -71, -43, and -15		
PD sampling			Х		Х		PD sampling is measurement of serum free C5 and total C5 concentration. Refer to Sections 8.5 and 8.6 for details		
Review safety card	Х	Х	Х	Х	Х	Х			
BTH	←Monitor continuously→			If a BTH event occurs during the Screening Period, the participant will be ineligible for the study. To confirm BTH, LDH, PK, and PD samples will be collected and analyzed. If the suspected event of BTH does not occur at a scheduled visit, an unscheduled visit should occur for evaluation of the participant and collection of the required LDH, PK, and PD samples.					
Concomitant medications		+	-Monitor c	ontinuously	$\rightarrow$				
Adverse events		÷	-Monitor c	ontinuously	$\rightarrow$				
Confirmation of eculizumab dose	X	X	X	X	X	Х	At the Investigator's discretion and preference of the patient, eculizumab may be administered at the participant's home (except at Visits -57 and -29) by a trained qualified staff member (Section 8)		

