# 8. STUDY ASSESSMENTS AND PROCEDURES

- Study procedures and their timing are summarized in the SoA (Section 1.3).
- Immediate safety concerns should be discussed with Alexion immediately upon occurrence or awareness to determine if the participant should receive the study drug.
- Adherence to the study design requirements, including those specified in the SoA, is essential and required for study conduct.
- During Screening, eculizumab may be administered at the participant's home at the discretion of the Investigator and preference of the patient, in accordance with the local procedures and Standard Operating Procedures at the site. These visits will be conducted by a trained qualified staff member. During a home administration visit, all assessments will be performed according to the SoA (Table 1). Patients must return to the study site for any visit at which PD sampling (Day –57 and Day –29) is scheduled, as specified in the SoA (Table 1). In countries where local legislation does not allow infusions outside authorized study sites, the Investigators will be notified in writing that this provision is prohibited
- All screening evaluations must be completed and reviewed to confirm that potential participants meet all eligibility criteria. The Investigator will maintain a screening log to record details of all participants screened and to confirm eligibility or record reasons for screening failure, as applicable.
- Procedures conducted as part of the participant's routine clinical management (eg, blood count) and obtained before signing of the ICF may be utilized for screening or baseline purposes provided the procedures met the protocol-specified criteria and were performed within the time frame defined in the SoA.

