# 8.10. Patient-Reported Symptoms and Health Resource Utilization questionnaires

Patient-reported PNH symptoms (PRS) and Health Resource Utilization (HRU) data, will be collected at Day 1 (baseline), Day 183 and Day 351/ET in the eCRF by the Investigator and study-site personnel for all participants throughout the study. Protocol-mandated procedures, tests, and encounters are excluded.

For PRS, each participant will record the presence or absence of the signs and symptoms of PNH: fatigue, chest pain, abdominal pain, dyspnea, dysphagia, headache, confusion, erectile dysfunction (if applicable), discoloration of urine, discoloration of eyes (see Appendix 10.5.1).

For HRU, the Investigator or designee will record for each participant the number of clinic visits, emergency services utilized, hospitalization, missed work and also record the number of times the participant had darkened urine (see Appendix 10.5.2).

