8.3.2. Healthcare Resource Utilization

For HRU, the Investigator or designee will record for each participant the number of clinic visits, emergency services utilized, hospitalization, missed work and also record the number of times the participant had darkened urine at baseline, Day 183, and Day 351/ET.

This document is confidential

SAP Version: 2.0 09-Feb-2023

Controlled Document ID: 3903A.02, Effective Date 31-Aug-2020

HRU data will be summarized descriptively by visit for the FAS. The summaries will include the proportion of participants who required healthcare resource utilization within a month before the specified study visit and the frequency of HRU.

All data will be listed.

9. Pharmacokinetics

All pharmacokinetic analyses will be conducted on the PK Analysis Set.

The non-compartmental analysis will be performed using appropriate software, ie, Phoenix™ WinNonlin® (Version 8.0 or higher, Certara Corporation) to report on the basis of this SAP.

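### HRU item 1 does not carry the Section 8.10 exclusion, and its one-month recall is shorter than the 8-week ravulizumab interval, so item 1 may not be comparable before and after the switch

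*Protocol*

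**What the plan says.** HRU data "will be collected at Day 1 (baseline), Day 183 and Day 351/ET in the eCRF" (Protocol 8.10). The form in Protocol 10.5.2 uses a one-month recall. Its first item reads "How many times within the past month have you visited your health care provider primarily for treatment of your PNH", and the respondent enters 0 if no physician was seen for PNH in that month. The form says nothing about leaving out infusion or study visits.

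Protocol 8.10 does: "Protocol-mandated procedures, tests, and encounters are excluded". SAP 8.3.2 does not repeat this. It plans a descriptive summary by visit on the Full Analysis Set of the "proportion of participants who required healthcare resource utilization within a month before the specified study visit", together with the frequency of use.

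On treatment before the switch, the synopsis states: "During screening, participants will continue to receive eculizumab 1200 mg q2w". Table 1 places these visits on Days -85, -71, -57, -43, -29 and -15, and notes that "eculizumab may be administered at the participant's home (except at Visits -57 and -29) by a trained qualified staff member". After the switch, Table 2 schedules ravulizumab on Days 1, 15, 71, 127, 183, 239 and 295, with no dose on Day 351.

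**The concern.** A visit made to receive an infusion is, on plain reading, a visit to a provider for treatment of PNH, so a respondent following the form would count it. A site following 8.10 would not. The two texts give different answers to the same question.

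The status of eculizumab in Screening adds a second ambiguity. Participants were already prescribed it, and Protocol 6.1 lists only ravulizumab as study drug. Yet each infusion day is also a scheduled visit in Table 1. A site could reasonably treat these visits as routine care and count them at Day 1, then leave out the ravulizumab visits as protocol-mandated.

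The recall period makes this matter. One month is longer than the 14-day eculizumab interval and shorter than the 56-day ravulizumab interval. Counted infusion visits would therefore appear at baseline and drop out later because of when the question is asked, on top of the real reduction in infusions. Fewer visits is a benefit that Protocol 2.3.2 expects, so a fall in item 1 would be easy to read as confirmation. The Day 183 data also enter the interim analysis, which is planned for publication and includes all tables, figures and listings (SAP 1.2 and 13).

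**Working it through.** **Inputs.** Visit days and windows come from Protocol Tables 1 to 3: ±2 days in Screening and ±7 days from Day 71 onwards and on q6w. There is no Day 0 (SAP 6.2). The documents do not define a month in days, so 28, 30 and 31 days are all tried.

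**1. Intervals.** The Screening visits are 14 days apart. The ravulizumab schedule from Day 15 onwards has gaps of 56 days. Both match the stated q2w and q8w.

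**2. Look-back from Day 1.** With no Day 0, days elapsed = 1 - (visit day) - 1.

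| Eculizumab visit | Days before Day 1 | With ±2 days |
|---|---|---|
| Day -15 | 15 | 13-17 |
| Day -29 | 29 | 27-31 |
| Day -43 | 43 | 41-45 |

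Day -15 is always inside the month and Day -43 never is. Day -29 is inside a 28-day month if it falls 27 or 28 days back, inside a 30-day month if 27 to 30 days back, and always inside a 31-day month. Infusions captured: 1-2, 1-2 and 2 respectively.

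Infusions are not the same as provider visits. Day -15 may be given at home, while Day -29 must be on site. If Day -15 is at home and Day -29 falls outside the month, the count is 0. Over all cases, infusion visits at baseline are 0-2.

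**3. Look-back from Day 183 and Day 351 on q8w.** 183 - 127 = 56 and 351 - 295 = 56. Shortest gap: (183 - 7) - (127 + 7) = 42. Longest gap: (183 + 7) - (127 - 7) = 70. The figures for Day 351 are the same. Since 42 exceeds 31, no earlier infusion is captured under any of the three month lengths.

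**4. Exceptions.**
- On q6w (Protocol 6.6.2) the gap is 42 days, or 28-56 with windows. Of the 15 × 15 = 225 combinations of window shifts, 1, 6 or 10 put the earlier infusion inside a 28-, 30- or 31-day month. These are counts of combinations, not probabilities.
- A supplemental or accelerated dose after breakthrough hemolysis (Protocol 6.6.1), a dose at an unscheduled visit, or an early-termination visit can also bring an infusion inside the month.
- Day 183 is itself a dosing day. Table 2 fixes the questionnaire before dosing only for the confirmation visit.

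**5. True rate against recorded rate, if infusion visits are counted.**

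| Month | q2w infusions | q8w infusions |
|---|---|---|
| 28 days | 28/14 = 2.00 | 28/56 = 0.50 |
| 30 days | 30/14 = 2.14 | 30/56 = 0.54 |
| 31 days | 31/14 = 2.21 | 31/56 = 0.55 |

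The true fall is 1 - 14/56 = 75% in every row. On regular q8w dosing, where any infusion visit was counted at baseline, the form would record 0 later, a fall of 100%. Only the last step, from about 0.5 per month to 0, comes from the recall period.

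**6. If infusion visits are left out at all three time points,** the schedule contributes 0 at each, and no change.

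**The case against.** The strongest reply is that Protocol 8.10 already deals with this. The Screening visits are listed in Table 1, adherence to the schedule is required, and Day -29 must be on site because pharmacodynamic samples are due. On that reading both drugs' scheduled infusion visits are protocol-mandated and drop out everywhere. In addition, 8.10 and SAP 8.3.2 have the investigator or designee record HRU, so those bound by 8.10 make the entries. This is a fair reading, and if every site follows it there is no distortion. It does not settle the matter: the form is titled a patient questionnaire, addresses the participant directly and omits the rule, and 8.10 does not mention eculizumab. Nothing in the SAP would show which reading a site used.

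Two stronger inferences are tempting, and the documents do not support them. One is that health-care use will fall purely as an artefact of the schedule. It need not: 8.10 may be applied, and about 75% of any counted fall in infusion visits would be real. The other is that a ravulizumab infusion can never fall within the recall month. The exceptions in step 4 show otherwise.

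The reply is also right about reach. Emergency room visits, darkened urine and work missed because of symptoms do not count infusions. Hospital admission would do so only if an infusion were given as an admission. HRU is exploratory, with no planned test, in an estimation study of about 20 participants.

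**Conclusion.** The point holds as an inconsistency with a bounded consequence. The form's wording admits visits that 8.10 excludes, the SAP does not resolve the conflict, and the status of Screening eculizumab visits is open. If infusion visits are counted, item 1 records 0-2 of them at Day 1 and, on regular q8w dosing, no earlier one at Day 183 or Day 351. A real reduction of about 75% could then be shown as about 100% and could not be separated from disease-driven visits. If only the ravulizumab visits are excluded, the imbalance remains.

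This rests on three assumptions: a month of 28 to 31 days, dosing on schedule within the stated windows, and at least some forms completed as worded. The documents do not show how sites actually completed them. No primary, secondary or safety conclusion depends on it.

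**What to change.** Add one sentence to item 1 of the form and to Protocol 8.10: *Do not count study visits or visits made only to receive eculizumab or ravulizumab, at any of the three time points.* Report infusion frequency before and after the switch separately, from the dosing records; SAP 7.5.1 and 7.6 already list eculizumab in Screening and ravulizumab exposure.

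For forms already completed without the instruction, do not subtract infusion visits. Item 1 is a bare count with no visit dates, so nothing can be matched. Where a site already applied 8.10, subtraction would remove genuine visits or produce negative counts. Instead:

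- report item 1 as recorded;
- state in SAP 8.3.2 that it may include infusion visits and is not comparable before and after the switch;
- show beside it the number of recorded infusions in each participant's look-back month.

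The cost is one sentence in two places, a short SAP statement and one derived count from data already collected. The downsides are a smaller apparent fall in HRU and the need to identify which forms were completed before and after the wording change.
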